### **10.2.3. TEAEs Leading to Study Treatment Discontinuation**

TEAEs leading to study treatment discontinuation are those with “Action Taken with Study Treatment = Drug Withdrawn” recorded in the CRF.

The following summaries of TEAEs leading to study treatment discontinuation (number and percentage of participants) will be provided across the cohorts using Safety analysis set:

- Summary of TEAEs leading to study treatment discontinuation by worst CTCAE grade (any grade, grade 3-4, grade 5) presented by SOC/PT
- Summary of treatment-related TEAEs leading to study treatment discontinuation by worst CTCAE grade (any grade, grade 3-4, grade 5) presented by SOC/PT

Jazz Pharmaceuticals, Inc.

JZP712-201 Statistical Analysis Plan - Protocol Amendment

2

The analyses will be conducted from the first dosing date of study treatment to the last date of the 30-day safety window.

All TEAEs leading to study treatment discontinuation will be included in a by-participant listing including but not limited to participant identifier, cohort, SOC, PT, start date, end date, severity grade, relationship to lorbinecetin, seriousness, and outcome of the AE using Safety analysis set.

#### **10.2.4. TEAEs Leading to Dose Modification**

TEAEs leading to dose modification (dose delay/reduction) are those with “Action Taken with Study Treatment = Drug Interrupted or Dose Reduced” recorded in the CRF.

The following summaries of TEAEs leading to dose modification (number and percentage of participants) will be provided across the cohorts using Safety analysis set:

- Summary of TEAEs leading to dose delay/reduction by worst CTCAE grade (any grade, grade 3-4 presented by SOC/PT
- Summary of treatment-related TEAEs leading to dose delay/reduction by worst CTCAE grade (any grade, grade 3-4) presented by SOC/PT

The analyses will be conducted from the first dosing date of study treatment to the last date of the 30-day safety window.

All TEAEs leading to dose modification will be included in a by-participant listing including but not limited to participant identifier, cohort, SOC, PT, start date, end date, severity grade, relationship to lorbinecetin, seriousness, and outcome of the AE using Safety analysis set.

#### **10.2.5. Deaths**

Deaths will be summarized descriptively across the cohorts:

- All deaths, reasons for death
- Deaths within 30 days of the last dose received (the 30-day safety window), reasons for death

A by-participant listing of deaths will be provided for all enrolled participants population, in which deaths within the 30-day safety window will be flagged.

#### **10.2.6. Adverse Events of Special Interest**

Not Applicable.

#### **10.2.7. Overall Summary of Adverse Events**

A general summary of AEs will be provided with the number and percentage of participants in the Safety analysis set who experienced the following types of events across the cohorts:

- Participants with any TEAE
- Participants with any Treatment-Related TEAE
- Participants with TEAE by Worst CTCAE Grade

Jazz Pharmaceuticals, Inc.

JZP712-201 Statistical Analysis Plan - Protocol Amendment

2

- Participants with any TEAE CTCAE Grade  $\geq 3$
- Participants with any Serious TEAE
- Participants with any Serious Treatment-Related TEAE
- Participants with any TEAE Leading to Death
- Participants with any TEAE Leading to Study Treatment Discontinuation
- Participants with any Treatment-Related TEAE Leading to Study Treatment Discontinuation
- Participants with any TEAE Leading to Study Treatment Reduction/Delay/Interruption
- Participants with any Treatment-related TEAE Leading to Study Treatment Reduction/Delay/Interruption

### 10.3. Laboratory Assessments

Blood and urine samples for the determination of hematology, clinical chemistry, coagulation, thyroid function, and urinalysis laboratory variables described in Table 6 will be measured and reported across the cohorts using Safety analysis set.

**Table 6: Protocol Specified Laboratory Tests**

Laboratory Tests	Parameter		
Hematology	Platelet Count	White blood cell count with differential Neutrophils Lymphocytes Monocytes	
	Red Blood cell Count		
	Hemoglobin		
	Hematocrit		
Biochemistry – A	Serum electrolytes (Na + , K + , Cl  )	AST/ALT	GGT
	AP	Total bilirubin (and direct if total is $> 1.5 \times$ ULN)	LDH
	Creatinine	CPK	Glucose (random)
Biochemistry – B	Albumin	Total protein	Ca Mg
Coagulation	PT/INR	PTT	
Pregnancy testing	Highly sensitive serum or urine hCG pregnancy test (as needed for women of childbearing potential)		

## Jazz Pharmaceuticals, Inc.

## JZP712-201 Statistical Analysis Plan - Protocol Amendment

2

Other Screening tests	Serology (HIV antibody, HBsAg, and hepatitis C virus antibody)
-----------------------	--

ALT=alanine aminotransferase; AP=alkaline phosphokinase; AST=aspartate aminotransferase; CPK=creatinine phosphokinase; GGT=gamma-glutamyl transferase; HBcAb=hepatitis B core antibody; HBsAg=hepatitis B surface antigen; hCG=human chorionic gonadotropin; HCV=hepatitis C virus; HIV=human immunodeficiency virus; LDH=lactate dehydrogenase; PT=prothrombin time; PTT=partial thromboplastin time; ULN=upper limit of normal.

For all hematology, coagulation and biochemistry tests, the laboratory values at baseline and each of the post-baseline assessments until EOT visit will be summarized and presented using descriptive statistics, along with the number and percentage of participants with tests not done.

For each of the post-baseline assessments, change between baseline and that assessment in a specific laboratory value will be calculated as follows,

Change in lab value = [Lab value at the post-baseline assessment] – [Lab value at baseline], and will be summarized and presented using descriptive statistics.

If the laboratory value is not done or missing at either baseline or a specific post-baseline assessment for a participant, change between baseline and that assessment will be treated as unknown. For each of the post-baseline assessments, the number and percentage of participants with unknown changes between baseline and that assessment will also be presented.

The non-protocol specified tests (if any reported), and urinalysis results will not be summarized; they will only be included in by-participant listings.

Data recorded by the laboratory will be converted to the International System of Units (SI) and summary tables will be generated using both SI and Conventional units.

Quantitative laboratory measurements reported as “< X”, i.e., below the lower limit of quantification (LLQ), or “> X”, i.e., above the upper limit of quantification (ULQ), will be converted to X for the purpose of quantitative summaries, but will be presented as recorded, i.e., as “< X” or “> X” in the listings.

Clinical laboratory results will be graded according to CTCAE criteria, CTCAE v5.0 criteria (Appendix 2). The frequency and percentage of participants with each CTCAE grade for each visit during the treatment period will be described by cohort. Both the scheduled and unscheduled assessments will be used to identify the worst post-baseline values.

Listings of all laboratory data with results reported using SI and Conventional units, normal reference ranges, and CTCAE grades (when possible) will be provided using Safety analysis set.

Pregnancy test results and other screening tests will be included in by-participant listings only.

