### 7.2.2. Post-Baseline

Post baseline evaluations are defined as evaluations taken after the date of the first dose of study treatment.

The post-baseline period is further characterized into:

- A treatment period, which is the time period from the date of the first dose to the date of the last dose of study treatment
- A 30-day safety follow-up period after the last dose of study treatment
- An OS follow-up period, which is the period following the 30-day safety follow-up period after the last dose of study treatment until participants die or withdraw consent or are lost to follow-up or the cohort closes. If a participant is to permanently discontinue study intervention before disease progression, the participant will be followed for survival by telephone visits every 3 months until at least 80% of participants in each cohort have died, withdrawn consent, or are lost to follow-up.

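### The by-visit table of CTCAE laboratory grades stops at the last dose, so it omits Day 8/15 results after the last infusion and the EOT visit

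*SAP*

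**What the plan says.** SAP 10.3 (Laboratory Assessments) grades laboratory results by CTCAE v5.0 and sets the by-visit output: "The frequency and percentage of participants with each CTCAE grade for each visit during the treatment period will be described by cohort".

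SAP 7.2.2 divides the post-baseline time. The treatment period is "the time period from the date of the first dose to the date of the last dose of study treatment". It is followed by a separate item: "A 30-day safety follow-up period after the last dose of study treatment".

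Three other windows bear on the same results:

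- Ungraded laboratory statistics, also in SAP 10.3: "the laboratory values at baseline and each of the post-baseline assessments until EOT visit will be summarized".
- TEAE, SAE, discontinuation and dose-modification tables (SAP 10.2.1 to 10.2.4): from the first dose through 30 days after the last dose.
- Absolute dose intensity (SAP 10.1.1): the weeks of treatment are counted with 21 days added to the interval between first and last dose, so the final cycle counts as treatment time.

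Directly after the by-visit sentence, SAP 10.3 adds: "Both the scheduled and unscheduled assessments will be used to identify the worst post-baseline values". SAP 7.2.2 places no cut at the last dose on that term: "Post baseline evaluations are defined as evaluations taken after the date of the first dose of study treatment". The SAP does not say in which table the worst values appear, or whether they are shown as grades.

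**The concern.** Protocol 2.3.1 names reversible myelosuppression as the main risk of lurbinectedin. Its low point comes after an infusion, and the Day 8 and Day 15 samples are there to catch it. A graded table that closes on the day of the last infusion cannot show what that infusion did to the counts.

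The same applies to many of the laboratory values that lead to stopping. A participant who fails the retreatment check (Protocol 5.5), or whose toxicity delay exceeds 3 weeks (Protocol 7.1), is judged on samples drawn after what turns out to be the last dose.

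The by-visit table is the only graded laboratory summary that SAP 10.3 specifies, and it is specified by cohort. A reader who relies on it would have an incomplete picture of hematologic toxicity, most of all for participants with short exposure.

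**Working it through.** The plan gives no figure on this point, so there is none to reproduce. The check counts scheduled hematology visits inside and outside the window.

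**Inputs**

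- Infusion on Day 1 of each 21-day cycle (SAP 5.2). Assumption: no delays.
- Post-baseline hematology visits (Protocol Table 3, SAP Appendix 1): Day 8 and Day 15 of Cycles 1 and 2, Day 1 of Cycle 2 and each later cycle, and EOT. From Cycle 3, Day 8/15 tests are done only after specified toxicities or dose adjustments (Protocol 8.3.4), so they are not counted.
- EOT at 30 days after the last dose, assumed to be performed. The schedule waives it where data from the previous 10 days exist, subject to an exception for worsening.
- Cycle 1 Day 1 is not post-baseline under SAP 7.2.2.

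**Formulas**

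For *k* cycles received, the last dose falls on study day L = 1 + 21(*k* − 1). In cycle *c*, Day 1 falls on 1 + 21(*c* − 1), Day 8 is 7 days later and Day 15 is 14 days later. EOT falls on L + 30. A visit is inside the treatment period if its day is ≤ L.

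| Cycles received | L | Scheduled visit days | Inside treatment period | Inside last dose + 30 days |
|---|---|---|---|---|
| 1 | 1 | 8, 15, 31 | 0 of 3 | 3 of 3 |
| 2 | 22 | 8, 15, 22, 29, 36, 52 | 3 of 6 | 6 of 6 |
| 3 | 43 | 8, 15, 22, 29, 36, 43, 73 | 6 of 7 | 7 of 7 |
| 6 | 106 | 8, 15, 22, 29, 36, 43, 64, 85, 106, 136 | 9 of 10 | 10 of 10 |

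Counting only the unconditional Day 8/15 visits, 0 of 2 are inside after one cycle, 2 of 4 after two, and 4 of 4 after three or more. If Day 8/15 tests were done in every cycle, 2(*k* − 1) of 2*k* would be inside: 4 of 6 for three cycles and 10 of 12 for six.

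**What the last value inside the window can show**

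From Cycle 2, infusion requires ANC ≥ 1.5 × 10⁹/L and platelets ≥ 100 × 10⁹/L within the 3 days before (Protocol 5.5, Table 4). Inclusion criterion 8 sets the same limits for entry. In SAP Appendix 2, Grade 2 starts below 1.5 for neutrophils and below 75 for platelets. The neutrophil and platelet values that cleared the last infusion are therefore Grade 1 at worst. The argument does not extend to hemoglobin: its 9 g/dL limit admits Grade 2 (below 10.0 down to 8.0 g/dL).

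**Alternative reading**

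If SAP 10.3 meant the Intervention Period of the schedule of activities, the final-cycle Day 8/15 visits would be inside and only EOT would be lost: 3 − 1 = 2 of 3, 6 − 1 = 5 of 6, 7 − 1 = 6 of 7 and 10 − 1 = 9 of 10. The SAP does not say this, and its own definition in 7.2.2 says otherwise.

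**The case against.** The strongest reply is that little is lost from safety reporting as a whole, and much of that stands. All laboratory data are listed with CTCAE grades where possible. Ungraded summaries run to EOT. Clinically significant laboratory changes must be recorded as AEs (Protocol 8.3.4), and TEAEs are tabulated by worst grade through 30 days after the last dose, with a separate table for those leading to discontinuation. The secondary safety endpoint is AEs and SAEs, and no decision rule depends on this table.

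These routes do not fully replace a graded summary. Ungraded statistics do not count participants at each grade, listings are not summaries, and AE recording depends on investigator judgement. SAP 10.2 specifies the AE tables across all cohorts combined, although SAP 7.1 promises safety by cohort as well. SAP 7.2.4 uses the latest retest when the same visit number is assigned, so a by-visit table can show a recovered value even inside the window.

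Four stronger readings are tempting, and the documents do not support them:

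- **All graded reporting stops at the last dose.** The sentence on worst post-baseline values has no such cut. The fair criticism is that no table is specified for them.
- **Every laboratory toxicity that ended treatment is missing.** Treatment can also end for toxicity that persists after two dose reductions, or for frequent delays (Protocol 6.7). Earlier episodes of that toxicity fall on or before the last dose and would appear.
- **Each participant loses one nadir.** From Cycle 3 the Day 8/15 tests are conditional, so for many participants no final-cycle nadir is measured.
- **The PFS medians in the protocol background (1.4 and 4.6 months) give the share of participants with a single dose.** They come from other studies' populations. Treating them as exponential time on drug would place many stops before day 21, when the first scheduled scan is at 6 weeks.

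The direction of any bias in the by-visit percentages is also unproven, because SAP 10.3 does not state their denominator.

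**Conclusion.** The point holds as an inconsistency of windows within the SAP. On the SAP's own definition, the by-visit graded table can miss the neutrophil and platelet nadir after the last infusion, and many of the values that led to stopping. The effect is large for participants who receive one or two cycles. From three cycles on it is one scheduled visit, EOT, plus any Day 8/15 tests triggered in the final cycle. A one-dose participant contributes no scheduled post-baseline grade.

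The counts rest on 21-day cycles without delay, an EOT visit performed at day 30, and the literal reading of the treatment period. How many participants stop after one or two cycles cannot be derived from the documents, so no overall proportion of lost results is given.

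Severity is minor to moderate. The table is descriptive, the data survive elsewhere, and the primary ORR analysis is untouched.

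**What to change.** In SAP 10.3, replace the restriction to the treatment period with: *after the first dose through the EOT visit or 30 days after the last dose, whichever is later*. Naming the EOT visit matters because it is allowed at 30 ± 7 days. A plain 30-day cut would drop EOT samples taken on days 31 to 37 after the last dose.

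Specify a table of worst post-baseline CTCAE grade, as a shift from baseline, over the same window, by cohort and overall, using scheduled and unscheduled values. This gives the existing sentence on worst values an output. State the denominator for the by-visit percentages.

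The cost is a few SAP sentences, one program window and one table, with no new data collection. Reported laboratory toxicity may look slightly less favourable. The change should be made before database lock.

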## 10.4. Vital Signs

Systolic blood pressure (mmHg), diastolic blood pressure (mmHg), pulse rate (beats/min), respiratory rate (breaths/min), body temperature (C) at baseline and each of the post-baseline assessments will be summarized and presented using descriptive statistics across the cohorts using Safety analysis set. For each of the post-baseline assessments, the change between baseline and that assessment in a specific vital sign will be calculated as follows:

Change in vital sign = [post-baseline assessment] – [baseline assessment],

Jazz Pharmaceuticals, Inc.

JZP712-201 Statistical Analysis Plan - Protocol Amendment

2

and will be summarized and presented using descriptive statistics.

If a specific type of vital sign is not done or missing at either baseline or a specific post-baseline assessment for a participant, change between baseline and that assessment will be treated as unknown. For each of the post-baseline assessments, the number and percentage of participants with unknown changes between baseline and that assessment will also be presented.

A listing of clinically significant abnormalities post baseline as judged by the investigator will be provided. For each participant and each vital sign, if there is at least one abnormal result, all results at all visits for that vital sign will be included in the listing.

The following values will be summarized:

- Systolic pressure < 60 or > 160 mmHg
- Diastolic pressure < 50 or > 100 mmHg
- Pulse rate < 40 or > 120 beats per minute
- Respiratory rate < 10 or > 40 breaths per minute
- Temperature < 36 or > 39 degrees Centigrade

All vital signs will be listed by participant using Safety analysis set.

## **10.5. ECG**

A single 12-lead ECG will be obtained during screening using an ECG machine that automatically calculates the HR and measures PR, QRS, QT, and QTc intervals. A by-participant listing including heart rate (beats/min, PR Interval (msec), QRS duration (msec), QT interval (msec), QTcB (msec), QTcF (msec), ECG Interpretation and any abnormal findings will be prepared using Safety analysis set.

## **10.6. ECOG Performance Status**

ECOG will be assessed at screening, on Day 1 of each cycle, and at EOT. The frequency and percentage of participants with each ECOG score level will be summarized by visit and across cohorts using Safety analysis set.

A listing of ECOG score for all participants will be provided using Safety analysis set.

## **10.7. Physical Examination**

A complete physical examination will be conducted at screening, on Day 1 of each cycle, and at EOT. Height will be collected at screening only. BSA will be recalculated on Day 1 of each treatment cycle and for any change (higher or lower) of the baseline value  $\geq 10\%$  the dose will be adjusted.

A listing of physical examination data for all participants will be provided using Safety analysis set. Listing will include height (screening value), weight, BSA, BSA change from baseline value for all post-baseline visits.

## Jazz Pharmaceuticals, Inc.

## JZP712-201 Statistical Analysis Plan - Protocol Amendment

2

## 10.8. AAGP

One blood sample for the evaluation of Alpha-1 Acid Glycoprotein (AAGP) will be collected at the end of the lubrinezdin infusion ( $\pm$  5 min) on Cycle 1 Day 1 (C1D1) from all participants. The serum AAGP will be summarized by cohort using Safety analysis set and analyzed using summary statistics such as mean, SD, median, minimum, and maximum values. A by-participant listing of serum AAGP data will be provided for each cohort using Safety analysis set.

For more information, contact the Office of the Vice President for Research and Economic Development at [contact] or [[contact]](mailto:[contact]).

For more information, contact the Office of the Vice President for Research and the Office of the Vice President for Student Affairs.

© 2019 Pearson Education, Inc.

---

Digitized by [contact]

© 2013 Pearson Education, Inc.

For more information, contact the Office of the Vice President for Research and Economic Development at [contact] or [[contact]](mailto:[contact]).

- [REDACTED]
- [REDACTED]

© 2019 Pearson Education, Inc.

Term	Percentage
Climate change	98
Global warming	95
Green energy	92
Carbon footprint	88
Sustainable development	85
Renewable energy	82
Emissions reduction	78
Green economy	75
Carbon tax	72
Carbon pricing	95

For more information, contact the Office of the Vice President for Research and Economic Development at [contact] or [[contact]](mailto:[contact]).

© 2013 Pearson Education, Inc.

© 2013 Pearson Education, Inc. All Rights Reserved. May not be copied, scanned, or duplicated, in whole or in part. Due to electronic rights, some third party content may be suppressed from the eBook and/or eChapter(s). Editorial review has determined that any suppressed content does not materially affect the overall learning experience. Pearson Education, Inc. reserves the right to remove additional content at any time if subsequent rights restrictions require it.

For more information, contact the Office of the Vice President for Research and Economic Development at [contact] or [[contact]](mailto:[contact]).

Jazz Pharmaceuticals, Inc.

JZP712-201 Statistical Analysis Plan - Protocol Amendment

2

[REDACTED]

[REDACTED]

[REDACTED]

## **12. PHARMACODYNAMIC ANALYSES**

Not applicable.

Jazz Pharmaceuticals, Inc.

JZP712-201 Statistical Analysis Plan - Protocol Amendment

2

## Appendix 1: Schedule of activities

Procedure	Screening (window)	Intervention Period [Days]							EOT (30± 7D after last dose) or E/D	OS telephone call every 3 months	Comments			
		C1		C2		≥ C3								
		D1	D8	D15	D1	D8	D15	D1						
											
 
• D-1 is the calendar day before C1D1.
 
• Screening assessments must be repeated if the first infusion of lurbinectedin is given outside the stated window.
 
• EOT is defined as 30 days after the last dose of lurbinectedin, unless the participant starts any subsequent anticancer therapy, in which case the EOT visit should be performed immediately before the start of new therapy.
 
• The EOT assessments will be performed if no recent data are available (ie, within the previous 10 days prior to the EOT visit) or if the last available data show a Grade ≥ 2 increase in AE severity.
 
			
Informed consent	X (-28 to -1)													
Inclusion and exclusion criteria	X (-28 to -1)										Note: for HRD-positive cohort, participants without mutational analysis results are not eligible for participation			
Demography	X (-28 to -1)													
Primary diagnosis and prior treatment(s)	X (-28 to -1)													
Medical and cancer history/past and current medical conditions	X (-28 to -1)													
Full physical examination including height, weight, and BSA	X (-7 to -1)	X		X		X	X				BSA will be recalculated on Day 1 of each treatment cycle. The dose will be adjusted if BSA change is ≥ 10% (higher or lower) of the baseline value. Height is only required at Screening.			

